2.1.6 RANDOMISATION

Randomization numbers will be generated in blocks, for the 3 study arms in a ratio of 5:5:2, as follows:

- R21/Matrix-M™ + DHA-PIP+PQ (Arm 1)
- R21/Matrix-M™ alone (Arm 2)
- DHA-PIP+PQ alone (Arm 3)

Study participants will be assigned the next available randomization number on the list, and thus will be randomly allocated to Group 1, 2, or 3. This is an open-label study. Participants and clinical investigators will not be blinded to group allocation.

3 ANALYSIS OF PRIMARY AND SECONDARY OUTCOMES

3.1 INCLUSION IN ANALYSIS

All patients who received at least one dose of vaccine will be included in the safety analyses. Patients lost to follow-up before the completion of the follow-up period assessments will be censored at the last day seen.

Exclusion

Given the incidence of malaria in the study area, it is highly unlikely that any volunteer became infected with any *Plasmodium* species during the trial. However, to exclude the remote possibility that a participant becomes infected we will screen participants for malaria at the time screening, Month 0, Month 1, Month 2, Month 3, and Month 6. The malaria screen consists of a RDT. The result will be available in <30 min. Subjects positive for malaria at screening or Month 0 will be excluded from participation in the study and will not be enrolled or vaccinated. Subjects positive for malaria at Month 1 or Month 2 would be withdrawn from further vaccinations. In the remote scenario that a volunteer becomes parasitaemic during the study results obtained from that point in time onward will be confounded by the immune response to the natural infection. Immunology results obtained during and after an episode of parasitaemia will be excluded from the immunology analysis. The results will be included in the safety analysis.

The results will be reported in two ways: a) excluding results for the out-of-window visit as specified in the protocol (analogous to the per protocol approach PP) and b) including the results analogous to an intention to treat ITT approach.

3.2 PRIMARY OUTCOME

The primary outcome measures will be:

- The safety of the investigational treatment in each group:
 - Occurrence of serious adverse events (SAEs) from the date of the first vaccination to 28 days after the last vaccination, according to the MedRA classification.
 - Occurrence of SAEs during the whole study period, i.e. during a 6 month follow up period from the receipt of first vaccination, according to the MedRA classification.
- For all the 3 groups, the concentration of antibodies against *Plasmodium falciparum* circumsporozoite (anti-CS antibody), one month after the first dose (at Study month 1), one month after the second dose (at Study month 2).

4 STATISTICAL METHODS

4.1 GENERAL CONSIDERATIONS

4.1.1 DATA CHECKS

Data for each variable including calculated changes from baseline will be summarised using descriptive statistics such as n, mean, median, minimum and maximum, to check for any values that are out of range

or implausible. Missing data will be identified and queried when preparing data for analysis.

4.1.2 BASELINE DATA

Patient demographic characteristics (age, gender, weight), and all other baseline information will be summarised for each treatment group.

Numbers (with percentages) for binary and categorical variables. The mean (standard deviation) will be presented for continuous normally distributed data. The median (interquartile or full range) for continuous variables will be presented. Highly skewed data that take a wide range of values (including very large values) will be log transformed for meaningful analyses.

There will be no tests of statistical significance conducted for differences between randomised groups on any baseline variables.

4.1.3 SCREENING AND RECRUITMENT FLOWCHART

A study flowchart showing numbers of participants screened, randomised and those who are available for the final analysis populations will be constructed. Reasons for drop-out or exclusions will be shown at each stage.

4.1.4 ANALYSIS POPULATION

Primary outcome analyses will be carried out on both the according to protocol (PP) and the intention to treat (ITT) population. The PP analyses will be the main strategy for the immunogenicity analyses. The safety outcomes will be ITT. In the event of some subjects not meeting the in-/exclusion criteria at baseline being erroneously enrolled in the study, a modified intention to treat analysis (mITT) will be considered. In that case, reasons for exclusions will be clearly documented and justified. In the intention-to-treat analysis, every participant randomized in the study (who receive the correct or incorrect study agent, one or more doses, and complete or incomplete doses) will be analysed, except if he/she did not receive any dose of the study vaccine or if no post-randomization data was collected for this participant.

The per-protocol analysis will compare participants according to the study agent/treatment actually received and will include only those participants who satisfied the inclusion/exclusion criteria, followed the protocol, and received complete, correct doses. The following non-compliant participants will be excluded:

- Participants included without meeting at least one inclusion criterion
- Participants included despite meeting at least one exclusion criterion
- Participants found non-compliant with the blood sampling schedule
- Participants vaccinated with the wrong study agent (non-compliance with the randomization code)
- Participants excluded from the intention-to-treat (mITT) analysis.

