5. STATISTICAL ANALYSES OF PRIMARY SAFETY ENDPOINTS

Safety analysis will be performed on patients allocated to receive vaccination. The percentage of subjects with at least one local AEs with at least one general AE (solicited and unsolicited) and with any AE during the 7-day or total follow-up period up to 28 days after the last vaccine dose and overall will be tabulated with exact 95% CI. The percentage of doses followed by at least one local AE (solicited and unsolicited), by at least one general AE (solicited and unsolicited) and by any AE during the 7-day or the total follow up period up to 28 days after the last vaccine will be tabulated with exact 95% CI. The same computations will be done for Grade 3 AEs, for any AEs considered related to vaccination and for any Grade 3 AEs considered related to vaccination. The percentage of subjects reporting each individual solicited local AE (any grade and Grade 3) and solicited general AE (any grade, Grade 3, any related, Grade 3 related, resulting in medically attended visit) during the 7-day follow-up period (Day 0-6) after each vaccine dose and overall will be tabulated for each group. Similarly, the percentage of doses followed by each individual solicited local and general AE will be tabulated, overall vaccination course, with exact 95% CI. For fever, the number and percentage of subjects reporting fever by half degree (°C) cumulative increments during the first seven days (Day 0-6) after each vaccine dose and overall will be tabulated. Similar tabulations will be performed for any fever with a causal relationship to vaccination and Grade 3 ($> 39.5^{\circ}\text{C}$) causally related fever. The percentage of subjects reporting unsolicited AEs from the date of the first vaccine dose up to 28 days after the last vaccine dose will be tabulated by group and by MedDRA preferred term with exact 95% CI. Similar tabulation will be done for Grade 3 unsolicited AEs, for any causally related unsolicited AEs and for Grade 3 causally related unsolicited AEs. The percentage of subjects reporting SAEs and pregnancies will be described in detail. The percentage of vaccinated subjects reporting AEs of specific interest (meningitis and pIMDs) will be described in detail.

Thus, in summary, the safety analysis will be as follows:

- Frequency (%) of occurrence of solicited local and general AEs within seven days (day of vaccination and six subsequent days) after each vaccination with exact 95% CI by group and severity.

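### Safety is set as ITT and no analysis tabulates a wrong-agent participant's adverse events under the agents actually received

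*SAP*

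**What the plan says.** SAP 4.1.4 says of the primary outcomes in general: "Primary outcome analyses will be carried out on both the according to protocol (PP) and the intention to treat (ITT) population". For safety in particular it says: "The safety outcomes will be ITT". The ITT set in that section covers randomised participants "who receive the correct or incorrect study agent, one or more doses, and complete or incomplete doses", "except if he/she did not receive any dose of the study vaccine or if no post-randomization data was collected for this participant".

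On the per-protocol (PP) set the same section says "The per-protocol analysis will compare participants according to the study agent/treatment actually received". Its list of exclusions then includes "Participants vaccinated with the wrong study agent (non-compliance with the randomization code" as a reason for removal. Protocol B6.7.4 has the same grouping rule and the same exclusion.

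Three further places bear on safety:

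- SAP 4.1.6 presents descriptive statistics for each measure by randomised group.
- SAP 5 opens: "Safety analysis will be performed on patients allocated to receive vaccination".
- SAP 3.1, like protocol B6.7.2, instead puts into the safety analyses anyone who had a vaccine dose. Neither says which arm's column that person goes in.

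The safety table in SAP 5 has three columns, one of them for the unvaccinated arm.

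**The concern.** The primary objective is the safety of the vaccine with and without concurrent antimalarials. That is a question about exposure, so an adverse event is most informative in the column for the agents the participant took. The plan foresees wrong-agent administration, since its ITT definition provides for it, but it has no safety tabulation in which such a participant appears under what was given. ITT leaves the event with the allocated arm. PP has the right grouping rule but removes the very people whom the rule would move. The per-dose tables in SAP 5 carry no separate rule, so they have the same gap.

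**Working it through.** No figure in the plan bears on this point. The check is a reading of the definitions, followed by an illustration.

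**Step 1: where does a wrong-agent participant appear?**

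| Rule | Location | Wrong-agent participant |
|---|---|---|
| ITT, stated for safety | SAP 4.1.4 | Kept if they had a vaccine dose and have post-randomisation data; column read as the allocated arm |
| PP | SAP 4.1.4; protocol B6.7.4 | Grouped by receipt in principle, but excluded |
| Modified ITT | SAP 4.1.4 | Not addressed; covers enrolment against the eligibility criteria only |
| Receipt of vaccine | SAP 3.1; protocol B6.7.2 | Included if vaccinated; column not stated |
| Allocation to vaccine | SAP 5 | Included if allocated to Arm 1 or 2 |

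No row places the participant under the agents received.

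**Step 2: an Arm 1/Arm 2 mix-up.** Inputs are 50 participants in each of Arms 1 and 2 (SAP 2.1.5). I assume that one Arm 2 participant is given the Arm 1 regimen and has one event, that nobody else has an event, and that everyone else qualifies for every set. Intervals are exact (Clopper-Pearson) 95%. With 0 events in n the upper limit is 1 − 0.025^(1/n). With x events the limits are the 2.5% quantile of Beta(x, n − x + 1) and the 97.5% quantile of Beta(x + 1, n − x).

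| Grouping | Arm 1 | Arm 2 |
|---|---|---|
| ITT, by allocation | 0/50 = 0% (0 to 7.1%) | 1/50 = 2.0% (0.1 to 10.6%) |
| By agents received | 1/51 = 2.0% (0.0 to 10.4%) | 0/49 = 0% (0 to 7.3%) |
| PP | 0/50 | 0/49 |

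Example of the formula: 1 − 0.025^(1/50) = 7.1%. The single event sits in Arm 2 under ITT, in Arm 1 by receipt, and in neither under PP. The intervals overlap almost completely, so one such error would not change a conclusion on its own.

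**Step 3: Arm 3.** An Arm 3 participant vaccinated in error is inside the set under SAP 3.1, because vaccine was received. The same holds under the ITT definition in SAP 4.1.4, because the person was randomised and had a vaccine dose. Under SAP 5 the person is outside it, because Arm 3 was not allocated to vaccination. The outcome depends on which definition governs, so no proportion can be computed from the text.

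**The case against.** The strongest reply is that the plan never says safety columns follow the randomised arm, and that SAP 3.1 and protocol B6.7.2 define the safety set by receipt. The first part is right: column assignment is inferred from the ITT label, the wording about incorrect agents, the randomised-group summaries and the contrast with PP. The second part settles who is included but not where they are counted, so it does not close the gap.

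Other replies limit the size of the problem, and they stand:

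- Arms 1 and 2 receive the same vaccine at the same dose, so a mix-up between them misplaces antimalarial exposure only.
- Arm 2 has no Day 1 or Day 2 visits, so a full swap to the Arm 1 regimen would need extra attendances, in an open-label, single-centre trial that keeps agent accountability records.
- Investigators assess each event's relationship to the vaccine and the antimalarials (protocol Appendix B, 1.5.2), and serious events and events of specific interest are described in detail. Important individual events would not be lost, although these provisions do not regroup the tables.

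A reader might infer two stronger points that the documents do not support. The first is that an erroneously vaccinated Arm 3 participant would turn the no-vaccine cell from 0/20 into 1/20. SAP 5 leaves Arm 3 out of the safety analysis. SAP 3.1 and the ITT definition would drop the other 19, who had no vaccine, so a denominator of 20 follows from none of the three. The second is that allocation grouping dilutes a between-arm safety contrast. The plan reports safety as percentages with exact intervals and specifies no between-arm safety test or estimate.

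**Conclusion.** The point holds as a gap in the safety tabulation rules. On the natural reading, wrong-agent participants' events are shown under the allocated arm or dropped, and no table shows them under the agents received. It applies most clearly to mix-ups between Arms 1 and 2, where each misplaced participant with an event is worth about 2 percentage points in an arm of 50. The expected effect is small, because misallocation should be rare; the documents give no rate, so its size cannot be estimated. The conclusion rests on reading ITT as grouping by allocation. If the sponsor intends otherwise, the SAP needs to say so. The three differing definitions of the safety set need to be reconciled on either reading.

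**What to change.** In SAP 4.1.4 and 5, define a single safety set. Reconcile it with SAP 3.1 (receipt of vaccine), the ITT statement in 4.1.4 and the allocation wording in 5. It must also be consistent with the three-column safety table, so that the place of Arm 3 is explicit. State that safety tables group participants by the study agents actually received, including how someone given a wrong agent at only some of the three rounds is classified, and list every misallocation. Leave the immunogenicity populations as they stand, with PP as the main analysis and ITT alongside.

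The cost is a few sentences in the SAP and no new data. The one downside is that safety and ITT denominators may differ by one or two participants, which the listing would explain.

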specimen collection**

Document No.: FTM ECF-033-01

Page 29 of 52

The investigators will permit authorized representatives of the sponsor, ethical committee(s), regulatory agencies, authorized individuals from, Jenner Institute and the monitors to examine (and when required by applicable law, to copy) clinical records for the purposes of quality assurance reviews, audits and evaluation of the study safety and progress.

B6.7 Data analysis

B6.7.1 Study Endpoints

We will assess the R21/Matrix-M™ recipients with regards to:

Safety: the occurrence of solicited and unsolicited AEs and SAEs (please see safety section)

Immunogenicity: (a) serum anti-CS IgG antibody titres responses to NANP and anti-CS antibody avidity, (b) cellular immunity.

B6.7.2 Inclusion in Analysis

All patients who received at least one dose of vaccine will be included in the safety analyses. Patients lost to follow-up before the completion of the follow-up period assessments will be censored at the last day seen.

B6.7.3 Immunology analyses

Given the incidence of malaria in the study area, it is highly unlikely that any volunteer will become infected with any Plasmodium species during the trial. However, to exclude the remote possibility that a participant becomes infected we will screen participants for malaria at screening, Month 0, Month 1, Month 2, Month 3, and Month 6. Participants positive for malaria at screening or Month 0 are excluded from participation in the study and will not be enrolled or vaccinated.

B6.7.4 Overall plan

Both intention-to-treat and per-protocol analyses will be carried out. In the intention-to-treat analysis, every participant randomized in the study (who receive the correct or incorrect study agent, one or more doses, and complete or incomplete doses) will be analysed, except if he/she did not receive any dose of the study vaccine or if no post-randomization data was collected for this participant.

The per-protocol analysis will compare participants according to the study agent actually received and will include only those participants who satisfied the inclusion/exclusion criteria, followed the protocol, and received three complete, correct doses. The following non-compliant participants will be excluded:

- Participants included without meeting at least one inclusion criterion
- Participants included despite meeting at least one exclusion criterion
- Participants found non-compliant with the blood sampling schedule

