**Research Proposal Submission Form
for a study involving human subject enrollment WITH
specimen collection**

Document No.: FTM ECF-033-01

Page 30 of 52

- Participants vaccinated with the wrong study agent (non-compliance with the randomization code)
- Participants excluded from the intention-to-treat analysis.
- No interim analysis is planned.

B6.7.5 Analysis of baseline characteristics

The demographic characteristics of enrolled participants will be compared by study group.

B6.7.6 Analysis of immunogenicity

The serum anti-CS antibody titre and avidity

The main analyses will involve the serum anti-CS antibody titre and avidity. These parameters will be measured at baseline and then at follow-up times longitudinally. During statistical analysis, we will assess whether a participant had a titre that is greater than 4 times that of the participant's baseline titre. Then we will compute the number of participants who had a titre of greater than 4 times their baseline titres and obtain a proportion of these for each group. These proportions of participants with >4-fold rise in titre from baseline will be compared between arms at each follow-up time. A Fisher's exact test will be used to compare the proportions of participants with >4-fold rise in titre from baseline between groups at each follow-up. These proportions will also be summarised graphically by arm to visually assess the differences between arms over-time. This will help to visually assess whether time modifies the effect of group.

Furthermore, the absolute titre values will be analysed and compared between groups. Since the distribution of these titre values will likely be highly skewed overtime, these values will be log-transformed and compared between arms at the different follow-up times. In order to revert back to the original scale (taking exponentials), the Geometric Mean Ratios (GMR) of the titres will be the measures of effect of interest that will be used to compared the log-transformed titres between the arms. The 95% confidence intervals for the Geometric Mean Ratios will be presented. The mean titre trends (on log-scale) over time will also be plotted by arm to assess whether there is a difference in trends of the titres between arms over time.

Tests of significance will be performed at 5% significance level. Analyses will be performed in Stata version 17 or higher. A separate detailed Statistical Analysis plan will be developed, finalized and signed before databased lock.

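### Read literally, the ITT exception excludes all 20 Arm 3 participants, contradicting the SAP's own three-arm outcomes and tables

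*SAP*

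**What the plan says.** **Intention to treat (ITT).** Protocol B6.7.4 and SAP 4.1.4 give the same rule: every randomised participant is analysed, "except if he/she did not receive any dose of the study vaccine or if no post-randomization data was collected for this participant".

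**Per protocol (PP).** Protocol B6.7.4 keeps participants who, among other conditions, "received three complete, correct doses", and its exclusion list includes "Participants excluded from the intention-to-treat analysis". SAP 4.1.4 has removed the number three from the dose condition and refers to the agent or treatment received. Its list opens with "The following non-compliant participants will be excluded" and ends with "Participants excluded from the intention-to-treat (mITT) analysis". The SAP makes PP the main strategy for immunogenicity.

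**Safety.** There are three statements:
- SAP 4.1.4: "The safety outcomes will be ITT".
- SAP 3.1, with the same sentence in Protocol B6.7.2: "All patients who received at least one dose of vaccine will be included in the safety analyses".
- SAP section 5: "Safety analysis will be performed on patients allocated to receive vaccination".

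Protocol B6.7.1 also frames the safety and immunogenicity assessment around vaccine recipients.

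**What the plan asks of Arm 3.** SAP 3.2 lists safety for each group, and antibody concentration for all three groups, as primary outcomes. SAP 4.1.6 promises descriptive statistics for every study measure by randomised group. The baseline table, the antibody and avidity tables and the safety table all carry a no-vaccine row or column. The sample-size text (Protocol B5.3, SAP 2.1.5) sizes Arm 3 for an antibody comparison with each vaccine arm.

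**The concern.** Arm 3 is given dihydroartemisinin-piperaquine (DHA-PIP) and primaquine, and no vaccine (Table 1 in both documents; Protocol B6.4.5). An exception defined by absence of a vaccine dose therefore removes the arm for following its allocation, not for any departure from it.

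Safety is the primary objective, and Arm 3 is the only drug-only background against which Arm 1's adverse events can be read. It is also the unvaccinated reference for the antibody response. If the population rules are applied as written, the no-vaccine cells of the safety table are empty. On the plain reading of the SAP's last PP bullet, so are those of the main antibody tables. If the analyst fills them, which is likely because the tables name the arm, that departs from a rule stated in two documents. In an open-label trial, membership of the analysis sets should not be left to judgement after data are available.

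**Working it through.** **Inputs.** 120 randomised at 5:5:2 (Protocol B6.1, SAP 2.1.5 and 2.1.6). Arm 3 vaccine doses: none (Table 1 in both documents). Drug schedule: Protocol B6.2 and Table 2.

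**1. The plan's own figures.** Arm sizes are 120 × 5/12 = 50, 120 × 5/12 = 50 and 120 × 2/12 = 20, as stated. Full enumeration of the two-sided Fisher exact test for 50% v 80% with 50 per arm gives 85.3% power, against the stated 85%.

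**2. The ITT exception.** All 20 Arm 3 participants have no vaccine dose, so 20/20 meet it. Excluded: 20/120 = 16.7%. Remaining: at most 50 + 50 = 100, and 100/120 = 83.3%. An Arm 3 participant would enter only if vaccinated in error.

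**3. Each stated population, by arm (maximum numbers).**

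| Rule | Arm 1 | Arm 2 | Arm 3 |
|---|---|---|---|
| ITT, Protocol B6.7.4 and SAP 4.1.4 | 50 | 50 | 0 |
| PP, Protocol B6.7.4 | 50 | 50 | 0 |
| PP, SAP 4.1.4, plain reading of last bullet | 50 | 50 | 0 |
| Safety, SAP 4.1.4 (ITT) | 50 | 50 | 0 |
| Safety, SAP section 5 (allocated vaccine) | 50 | 50 | 0 |
| Safety, Protocol B6.7.2 and SAP 3.1 | vaccinated included | vaccinated included | not addressed |

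The last row names who is included and does not expressly exclude anyone else, so it neither removes Arm 3 nor brings it in. The third row is less certain than the second: the SAP bullet says mITT in parentheses, and its list is headed as one of non-compliant participants, which compliant Arm 3 participants are not. The mITT option itself concerns ineligible enrolments and can only remove people.

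**4. PP dose condition.** Arm 3 is scheduled for 3 rounds × 3 daily doses = 9 DHA-PIP doses, plus 3 primaquine doses and no vaccine dose. The Protocol's count of three fits the vaccine course but not that regimen. The SAP no longer contains the number, so this remains a problem in the Protocol only.

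**5. The two restrictive safety rules compared.** An Arm 1 participant who took the drugs but no vaccine is in under SAP section 5 (allocated to vaccine) and out under SAP 4.1.4 (ITT). The rules disagree even within the vaccine arms.

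**6. Safety windows.** The solicited, unsolicited and per-dose windows (Protocol B6.3.1 and Appendix B 1.6; SAP section 5) run from vaccination. Arm 3 has no vaccination date, so admitting it to the population would not by itself define its windows.

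**7. Arm 1 versus Arm 2.** The exception removes an unvaccinated participant from either arm alike, so this 50 v 50 comparison is unchanged.

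**The case against.** The strongest reply is that the intent is plain. The outcomes, the descriptive instruction and the tables all name a no-vaccine group, and no analyst would leave those cells blank. That largely stands: this is a defect of wording. It does not remove the need for correction, because the intent can be followed only by departing from the written rule.

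A second reply is that safety may deliberately cover vaccine recipients only. The primary objective is the vaccine's safety, and Protocol B6.7.1 and SAP section 5 point that way. This has force, and it is why the passages need reconciling. On that reading, however, the no-vaccine column of the safety table and the each-group outcome in SAP 3.2 are wrong, so some text must change either way.

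A third reply is that the SAP has already repaired the PP dose rule by dropping the number three. That is correct; what remains in the SAP is the ambiguous last bullet.

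Three stronger readings are tempting and not supported:
- A reader might infer that the plan simply drops Arm 3, or that every stated population excludes it. The at-least-one-dose statement does not exclude anyone, and other passages require Arm 3. The plan contradicts itself.
- A reader might infer that the main immunologic comparison is compromised. The objective compares Arms 1 and 2, which the exception treats alike.
- A reader might infer that the piperaquine comparison loses Arm 3. The remark to Protocol Table 9 says drug levels will be assessed in the 20 drug-only participants, and neither document names a separate population for that comparison. The loss is not established.

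**Conclusion.** The concern holds as a contradiction in the population rules. Taken literally, the ITT exception excludes 20 of 120 randomised (16.7%), which is the whole of Arm 3. The Protocol's PP set follows outright, and the SAP's PP set follows on the plain reading of an ambiguous bullet. The two restrictive safety rules leave Arm 3 out, and the third safety statement does not bring it in. This conflicts with SAP 3.2, SAP 4.1.6, the table shells and the sizing of Arm 3.

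The counts assume full enrolment at 50/50/20 and no Arm 3 participant vaccinated in error. They describe who is eligible for analysis, not a bias in any estimate. Because the intent to report Arm 3 is fairly clear and Arm 1 versus Arm 2 is untouched, this should be fixed before database lock but does not threaten the trial.

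**What to change.** 1. **ITT (Protocol B6.7.4, SAP 4.1.4).** Make the exception arm-specific. For Arms 1 and 2, keep exclusion of those with no dose of study vaccine. For Arm 3, exclude those who received neither DHA-PIP nor primaquine. The simpler edit, any dose of any study agent, should be avoided: it would keep an unvaccinated Arm 1 participant who took the drugs while dropping an unvaccinated Arm 2 participant.
2. **PP.** Carry the SAP's dose wording into the Protocol as complete, correct doses of the allocated agent or agents. State whether the last SAP bullet means ITT or mITT.
3. **Safety.** Reconcile Protocol B6.7.1 and B6.7.2 and SAP 3.1, 4.1.4 and 5 with SAP 3.2 and the no-vaccine column of the safety table, so that one stated population supports the three-arm table. Count Arm 3's adverse-event windows from Day 0 of each drug round.
4. **Separate endpoint discrepancy.** Reconcile Protocol B6.3.2, which lists the antibody endpoint for Arms 1 and 2, with SAP 3.2, which lists it for all three groups.

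The cost is a wording change to the analysis sections of both documents before lock. No new data, visits or samples are needed: Arm 3 already attends Days 0, 1, 2 and 7 of each round (Protocol Table 6), and each participant is given a diary card (Protocol B6.4.5).

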This study is a randomized, open-label, single centre, Phase 2 trial of R21/Matrix-M™ in healthy Thai adults. A total of 120 participants will be enrolled and randomized into one of three study arms in a ratio of 5:5:2 as described in Section 6.4.4. Each arm will have 50 participants (for arm 1 and 2) and 20 participants (for arm 3).

- For arm 1 and 3, the eligible volunteers will be asked to come into the Hospital for Tropical Diseases to receive the study agents as out-patient on Day 0 (the day of vaccination), Day 1, Day 2, and Day 7 of Study Months 0, 1 and 2; and on Day 0 of Study Months 3 and 6. There are a total of 15 study visits.
- For arm 2, the eligible volunteers will be asked to come into the hospital to receive the study agent (vaccination only) as out-patient on the day of vaccination (Day 0) and Day 7 of Study Months 0, 1 and 2; and on Day 0 of Study Months 3 and 6. There are a total of 9 study visits.

**Research Proposal Submission Form
for a study involving human subject enrollment WITH
specimen collection**

Document No.: FTM ECF-033-01

Page 16 of 52

Table 2. Vaccine and drug administration

Timepoints	Month Day of month	Scr.	Study period														
			M0				M1				M2						
			0	1	2	7	0	1	2	7	0	1	2	7			
Interventions	Vaccination (Group 1 and Group 2)		x					x						x			
	DHA/piperaquine (Group 1 and Group 3)		x	x	x			x	x	x				x	x	x	
	PQ (single low dose primaquine) (Group 1 and Group 3)		x					x						x			

B6.2 Investigational Products:

1) R21/Matrix-M™

Description of Vaccine: The candidate R21 vaccine to be used has been developed by Jenner Institute and manufactured under cGMP conditions at Serum Institute India Private Limited (SIIPL). R21 is produced to high levels in *Hansenula polymorpha* yeast in fermenters. The purified R21 antigen (drug substance) is released after testing, by SIIPL QC Department using qualified and validated methods. The quality released drug substance is used, for manufacturing drug product after appropriately diluting to 20 µg/mL using formulation buffer. The formulated blend is fill finished in siliconized glass vials (4 mL capacity) at a targeted concentration of not less than 20 µg/mL. Each vial is filled with 0.65 mL of the drug product to enable withdrawal of 0.5 mL. The final formulation has 20 mM Tris, 15% sucrose, 30 mM magnesium chloride, pH 7.4.

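### The per-protocol set, the main one for immunogenicity, is defined by two conflicting rules, and the participant-level rule discards in-window early titres because of later events

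*SAP*

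**What the plan says.** SAP 4.1.4 (Analysis population) states: "The PP analyses will be the main strategy for the immunogenicity analyses". Its list of people to leave out of that set includes "Participants found non-compliant with the blood sampling schedule", and Protocol B6.7.4 (Overall plan) has the same item. Neither place says which draws make up the schedule or how many deviations make someone non-compliant.

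SAP 3.1 (Inclusion in analysis) works at the level of the visit. Results are to be reported once "excluding results for the out-of-window visit as specified in the protocol (analogous to the per protocol approach PP") and once with the out-of-window results kept in, which it likens to ITT.

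The dose condition also differs. Protocol B6.7.4 requires that the participant "followed the protocol, and received three complete, correct doses". SAP 4.1.4 requires that the participant "followed the protocol, and received complete, correct doses", with no number and no statement of whether antimalarial doses count alongside vaccine doses.

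**The concern.** Two statisticians following this plan could build different PP sets and report different main results for Arm 1 against Arm 2. The trial is open-label, so this choice should be fixed in writing before the data are seen.

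The response is compared separately at Months 1, 2, 3 and 6. Under the participant-level rule, a person with a good baseline and a good Month 1 sample drops out of the Month 1 comparison because of a draw missed at Month 6. Where three doses are required, stopping before dose 3 has the same effect. Early endpoints are then conditioned on later behaviour, and usable titres are set aside.

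The second issue is balance between arms. Pharmacokinetic (PK) samples are taken only in Groups 1 and 3. If those bleeds belong to the schedule, Arm 1 has more occasions on which to fail than Arm 2.

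**Working it through.** **Inputs from the documents**
- Arms 1 and 3: "There are a total of 15 study visits" (Protocol B6.1). Arm 2 has 9. Both counts include screening.
- Removing screening and M0 Day 0, the day of enrolment and allocation, leaves 13 visits in Arm 1 and 7 in Arm 2. Table 5 schedules blood at all of them.
- The six extra Arm 1 visits are Days 1 and 2 of Months 0, 1 and 2.
- Immunology samples: baseline plus Months 1, 2, 3 and 6 in both arms, so 4 after baseline.
- Windows (Table 7): Day 7 ±1 day, monthly visits ±7 days, Month 6 ±14 days. None is listed for Day 1 or Day 2.
- Power basis (SAP 2.1.5): 50% v 80%, 50 per arm, Fisher's exact test, 5% level, 85% power. Replacement is attempted for withdrawals. There is no allowance for PP exclusions.

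**Assumption, not in the documents.** Each visit is missed or out of window with probability q, independently and equally in both arms. Values of 1%, 2% and 3% are shown.

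**Step 1: the plan's own figure.** Full enumeration of the two-sided Fisher test at 50/50, 50% v 80%, gives 85.3%. The stated 85% reproduces.

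**Step 2: participant-level rule.** Share retained = (1−q)^k, where k is the number of visits that count. Evaluable n = 50(1−q)^k, rounded. Power is then recomputed by the same enumeration.

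All bleeds count (k = 13 in Arm 1, 7 in Arm 2):

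| q | Excluded, Arm 1 v Arm 2 | n | Power |
|---|---|---|---|
| 1% | 12.2% v 6.8% | 44/47 | 83.2% |
| 2% | 23.1% v 13.2% | 38/43 | 78.8% |
| 3% | 32.7% v 19.2% | 34/40 | 74.5% |

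For example, at 2%: 1 − 0.98^13 = 0.231 and 1 − 0.98^7 = 0.132.

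Only immunology bleeds count (k = 4 in each arm):

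| q | Excluded, each arm | n | Power |
|---|---|---|---|
| 1% | 3.9% | 48/48 | 83.1% |
| 2% | 7.8% | 46/46 | 81.9% |
| 3% | 11.5% | 44/44 | 80.2% |

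**Step 3: in-window results discarded at q = 2%, all bleeds counting.** About 50 × 0.98 = 49 Month 3 results per arm are in window. The participant-level rule discards those with a deviation at any other visit: 49 × (1 − 0.98^12) = 10.5 in Arm 1 and 49 × (1 − 0.98^6) = 5.6 in Arm 2. If only immunology bleeds count, it is 49 × (1 − 0.98^3) = 2.9 in each arm.

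**Step 4: visit-level rule at q = 2%.** With baseline present and doses taken, 49 per arm remain at each timepoint, and power is 84.2%.

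**The case against.** A reader might infer that the plan necessarily removes more of Arm 1 than Arm 2. The documents do not support that. They nowhere say that the schedule covers every draw. If it means the immunology samples, the sampling clause treats the arms alike. Even where the loss is unequal, nothing in the documents says which way the response rates would shift.

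It is also tempting to say that the extra Arm 1 draws have nothing to do with the antibody comparison. That goes too far. Days 1 and 2 are antimalarial dosing days, and blood is taken before each dose. A participant who misses such a visit has normally missed a dose as well, which may breach the dose condition whatever the sampling clause says. The antimalarial is also the exposure being compared. This objection stands, and it shows that the undefined dose condition matters as much as the undefined schedule.

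Three further points stand in part:
- No document gives a miss rate. Misses tend to cluster within people, which would make the losses smaller than independence implies. The lack of a Day 1 or Day 2 window also makes a common rate approximate.
- ITT is planned alongside PP, SAP 3.1 also reports with out-of-window results included, and the flowchart will show reasons for exclusion. The data are therefore not lost to the trial. PP is nevertheless the named main strategy, so its definition decides the main result.
- Requiring a complete schedule is a conventional PP definition. That does not settle which of the two rules applies here.

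**Conclusion.** The conflict is in the text and does not depend on any assumption: a visit-level rule in SAP 3.1, a participant-level rule in SAP 4.1.4 and Protocol B6.7.4, and a dose condition that specifies three doses only in the protocol. It also follows directly that the participant-level rule discards in-window early titres because of later events.

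The arm imbalance is conditional. If PK and safety bleeds count and per-visit compliance is similar, Arm 1 can be expected to lose more than Arm 2 at any miss rate strictly between 0 and 1. The size rests on the assumed rate and on independence. If only immunology bleeds count, the sampling clause is symmetric and the loss is modest, with power still about 80% or more for rates up to 3%.

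The stated 85% power is not an error. It applies to 50 evaluable per arm. This should be corrected before database lock, but it does not undermine the design.

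**What to change.** Write one timepoint-specific PP rule and use it in SAP 3.1, SAP 4.1.4 and Protocol B6.7.4. For each timepoint, include eligible participants who received, as randomised, the study doses due before that visit, and who have a baseline sample and an in-window immunology sample for that visit. On the existing schedule this means the first dose for Month 1, the first two for Month 2, and all three for Months 3 and 6.

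In addition:
- State that a missed PK or safety-laboratory sample does not by itself exclude anyone from the immunogenicity analysis.
- State whether the dose condition covers vaccine doses only or antimalarial doses as well, and reconcile the protocol and SAP wording. If antimalarial doses count, Arm 1 may still lose more than Arm 2, and the report should say so.
- Report exclusions by arm, timepoint and reason.

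The cost is a wording change in the SAP, a matching change in the protocol, and one derived flag per timepoint. The drawback is that the PP denominator differs between visits.
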